
study, the most valued aspect of the program was interaction with their peers, which informs the proposed intervention.

4. The Peer Approaches to Lupus Self-Management (PALS) Pilot Study. The PALS intervention was piloted with African American women with lupus enrolled in the SLE database at MUSC. Seven mentors were trained and paired with 21 mentees to provide modeling and reinforcement to participants by telephone for at least 60 minutes every week for 12 weeks. Mentee outcomes of self-management, disease progression (including disease activity, damage, and cytokine balance) were obtained at baseline, mid-intervention (6 weeks from baseline), and immediately postintervention (12 weeks from baseline), using validated tools. Qualitative data were also collected over the course of the study in the form of weekly mentee check-ins, mentor logs, and an end-of study focus group. While the PALS pilot lacked a control group, it provided a sense of general effect size and was used to design the current study.[107,108] At post-intervention, we observed statistically significant decreases in patient-reported disease activity (significant change score of 24,70 or 25% change in patient global assessment of overall lupus disease activity, p<0.001). incrementally improving trends in patient activation, and statistically significant decreases in depression (significant change score of 2.62 or 11% change in PHQ-8 score, p=0.05) and anxiety (significant change score of 3.52 or 15% change in GAD-8 score, p=0.018). Student t tests were also conducted to compare 2-month pre- and 2-month post-intervention hospitalization charges. Mean charges per person were \$24289 prior to intervention and \$872 post intervention, providing very strong evidence for the intervention's potential to reduce inpatient charges post intervention.[109] In addition, both mentees and mentors gave very high scores for perceived treatment credibility and service delivery, providing preliminary support for the efficacy, acceptability, and perceived credibility of the PALS intervention.[87,88,97] In summary, our preliminary studies demonstrate that in African American women with SLE, selfmanagement education delivered in weekly sessions led to improvements in lupus self-efficacy, health distress, and depression, and that more culturally targeted information and increased social support could yield more significant improvements in quality of life. More importantly, results of BLESS and IQAN studies, feedback from patients, extensive review of the literature and preliminary data from the PALS pilot study suggest that a peer mentoring intervention is credible, acceptable and likely to be effective at improving self-management, decreasing disease activity and improving quality of life in African American women with SLE. Additionally, using the same outcome measures across investigations will allow comparison of the impact of the current culturally tailored approach to the untailored "Better Choices, Better Health" intervention used in the BLESS study with this patient population.

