intervention can be compared with any changes in MUSC health services utilization costs for emergency department, inpatient and outpatient care for the intervention relative to the control group. In addition to a comparison of intervention cost with average difference between MUSC costs for intervention and control group 12 months post baseline, generalized linear cost models can be estimated to examine the association of the treatment with MUSC health services costs while adjusting for patient demographics (age, gender, race/ethnicity, co-morbidities) and clinical outcomes. MUSC does not provide cost information, only charges. In addition we will estimate the impact on work loss and income by estimating the changes in days lost to illness and income based on values provided by participants. We will use the year for which the hospital charge and income data is reported and adjust for inflation as appropriate using the US Department of Labor Consumer Price Index. Inpatient and outpatient MUSC costs will be compared separately and together between the control and intervention groups. Bootstrapping methods will be used to conduct sensitivity analyses for all cost models. Sensitivity analysis will be performed by estimating a separate MUSC health services cost model while adjusting for each clinical outcome to insure robust results regarding the marginal effect of the treatment on MUSC health services costs. Park tests will be conducted to determine the best fit for the cost data in specifying the generalized linear model. In the event of many zero values, a two-part model will be used to first examine the association of the treatment with the likelihood of any MUSC costs and then the conditional generalized linear cost model, conditional on having non zero MUSC cost value for the patient. The ICR will be reported as a single ratio with no uncertainty attached to it. Therefore, standard statistical characteristics such as confidence intervals or hypothesis test to compare it to an a priori ICR from another study are not applicable. We will calculate the ICR and a clinically relevant interpretation of the outcome will be p Human Subjects Involvement and Characteristics. The Peer Approaches to Lupus Self-Management (PALS) study is a randomized controlled trial designed to examine whether a new, culturally tailored peer mentoring intervention improves disease self-management, indicators of disease activity, and health related quality of life (HRQOL) in African American women with systemic lupus ervthematosus (SLE). African American women with active SLE will be recruited as mentees and peer mentors who are considered competent in the management of their condition will be identified and recruited to provide modeling and reinforcement to participants. We will recruit mentees for 300 observations (150 mentored and 150 support group) and up to 60 mentors. Mentees and mentors will be primarily recruited from the longitudinal web-based SLE database at the Medical University of South Carolina (MUSC) in three cohorts. As part of each cohort, mentors (n=20) will be trained to deliver intervention content, prior to being paired with up to three mentees (n=50). The peer mentoring intervention will occur by twelve 60minute telephone or video sessions carried out across the course of 24 weeks. In each cohort, social support controls (n=50) will participate in a lupus support group created for this project, on the same schedule as peer mentoring sessions. All participants (mentees, mentors, and social support controls) will be assessed using validated measures of patient reported outcomes and biological indicators of disease activity at baseline, mid-intervention (3 months from baseline), immediately post-intervention (6 months from baseline), and 6 months post-intervention (12 months from baseline). For each cohort, outcomes for mentees randomized to the mentored group will be compared with the outcomes of mentees randomized to the social support control group. A booster session will be incorporated for mentored participants at 3 months post-intervention to encourage retention.

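### When many costs are zero, the Aim 3 two-part cost model is described only as two separate parts, so the adjusted analysis gives no overall effect of treatment on MUSC costs

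*Combined protocol and SAP*

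**What the plan says.** The cost models are in the AIM 3 text of the Overview of Statistical Analysis Plan. The target is stated twice: "generalized linear cost models can be estimated to examine the association of the treatment with MUSC health services costs", and a sensitivity analysis is meant to secure "robust results regarding the marginal effect of the treatment on MUSC health services costs". Both refer to costs overall, not to costs among women who used services.

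The fallback has a trigger without a threshold, "In the event of many zero values". It has two steps. The first relates treatment to whether a woman has a MUSC cost at all. The second is worded as follows: "then the conditional generalized linear cost model, conditional on having non zero MUSC cost value for the patient". The description stops there. No section multiplies the two parts, predicts mean cost by arm, or gives a combined effect with an interval.

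Other statements in the same section bear on the point:
- An average difference in MUSC costs between the arms at 12 months is planned separately.
- "Inpatient and outpatient MUSC costs will be compared separately and together between the control and intervention groups".
- Bootstrapping is planned as a sensitivity analysis for all cost models.
- The models adjust for demographics, comorbidities and clinical outcomes.
- The incremental cost-effectiveness ratio (ICR) uses the arm difference in cost and is reported without uncertainty.

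**The concern.** Mean cost per woman is the product of two factors: the probability of any cost and the mean cost among women who have some. Each part of the model reports one factor. Neither is the effect on costs that the section says it wants.

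The second part has a further difficulty. Whether a woman has any MUSC cost is settled after randomisation, and mentoring may change it. Restricting to women with a non-zero cost gives up the comparison of the arms as randomised, although B4c (Scientific Rigor) promises intent-to-treat analyses. If mentoring prevents the cheaper episodes, the remaining users are the costlier ones. The second part can then suggest that mentoring raises costs while the total is unchanged or lower.

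The trigger is plausible. Inpatient costs are to be compared on their own, and some women will have no admission in a year. The mentee recruitment section admits women from outside the MUSC system, who may have no MUSC charges. The pilot's case for savings used t tests to "compare 2-month pre- and 2-month post-intervention hospitalization charges" ($24289 against $872 per person), an outcome where zeros are likely.

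**Working it through.** **No plan figure to reproduce.** The documents give no sample size, effect, zero share or variance for the cost models. What follows illustrates how the two parts behave.

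**Inputs from the documents.** 150 women per arm (B4b, Study Overview). Two-sided 5% level, which is stated under Aim 1; none is stated for the cost models.

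**Assumptions.** Shares of women with any cost as shown below. Gamma-distributed costs among users with a coefficient of variation (CV) of 1.0 or 1.5. No covariates, clustering or dropout.

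**Formula.** In each arm, mean cost per woman = P(any cost) × E(cost | any cost). With the control users' mean set to 1:
- a1: control 0.50 × 1 = 0.50; mentored 0.40 × 1.25 = 0.50. No difference.
- a2: control 0.50; mentored 0.35 × 1.43 = 0.50. No difference.
- a3: control 0.30 × 1 = 0.30; mentored 0.20 × 1.5 = 0.30. No difference.
- b: control 0.50; mentored 0.25 × 1 = 0.25. A 50% saving, all from fewer users.
- c: control 0.50; mentored 0.28 × 1.25 = 0.35. A 30% saving.

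**Tests.** Part 1: log odds of any cost. Part 2: log ratio of mean cost among users. All women: log ratio of mean cost including zeros, which equals the recombined result when treatment is the only term. There were 3,000 simulated trials per scenario; repeat runs differ by one or two percentage points.

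| Scenario | True ratio of mean cost | Part 2 significant (CV 1.0 / 1.5) | All-women mean significant (CV 1.0 / 1.5) |
|---|---|---|---|
| a1 | 1.00 | 25% / 15% | 4.5–6.6% across a1–a3 |
| a2 | 1.00 | 52% / 28% | as above |
| a3 | 1.00 | 42% / 23% | as above |
| b | 0.50 | 6–7% | 78% / 56% |

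Further results:
- In a1–a3, part 2 is significantly up and part 1 significantly down in the same trial in about 6% to 37% of trials (up to 40% in a repeat run).
- In b, part 1 is significant in over 99% of trials. It reports a change in the odds of any cost, not an amount saved.
- In c, the part 2 estimate points to higher cost while the observed total falls in 80% (CV 1.0) or 64% (CV 1.5) of trials. Counting only significant part 2 increases, this is 16% or 4%.
- The pattern also holds when more mentored women have costs. With 60% v 75% users and users' means of 10,000 v 8,000, both arms average 6,000. At CV 1.5, part 1 is significant in 80%, part 2 in 19% and the all-women mean in 5.0%.

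**The case against.** **Recombination may be intended.** The plan names a two-part model and a marginal effect, and combining the parts is the usual way from one to the other. A reader might infer that the plan decided to keep the parts apart, or to draw a cost conclusion from the second alone. The text supports neither: it omits the step and does not refuse it. It also speaks of examining associations and sets no decision rule for these models. The omission stands, because two analysts following the text could report different treatment results.

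**An all-women comparison already exists.** A reader might infer that the plan has no cost comparison over all women, or that the ICR is affected. That is not so. The average MUSC cost difference and the ICR cost term do not depend on the two-part model, and the well-behaved last column of the table is in effect that planned comparison. What is missing is narrower: an adjusted overall effect with stated uncertainty.

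**Savings from fewer users would not go unseen.** Part 1 finds them in scenario b with more power than the all-women mean, and part 2 is rightly null there because users' mean cost did not change. This is correct; what remains is that neither part gives the size of the saving.

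**Significant parts are not false positives.** In a1–a3 at least one part is significant in 51–89% of trials, but both part-wise null hypotheses are false there and the offsets were chosen to cancel. With no effect on either part the figure is 10–11%, ordinary multiplicity from two tests. The difficulty is reading either part as an answer about total cost.

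**The reach is conditional.** The fallback is tied to any MUSC costs, so its use for inpatient costs alone is an inference.

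**Conclusion.** The point holds as an omission. When zeros are many, the written adjusted analysis stops at two component effects, one of them in a subgroup formed after randomisation, and gives no overall effect of treatment on MUSC costs. The separate unadjusted difference covers all women, but has no stated interval, and the ICR carries no uncertainty.

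With equal true totals and 150 per arm, the second part alone is significant in about 15–50% of trials, and the two parts are significant in opposite directions in about 6–37%. These sizes rest on assumed zero shares, CVs and offsets, so they show what can happen, not what is expected here. The mismatch between target and model does not depend on them. Aims 1 and 2 and the ICR point estimate are unaffected.

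**What to change.** State in the Aim 3 text that the treatment result of the two-part model is the recombined difference in mean MUSC cost:
1. For every randomised woman, predict P(any cost) × E(cost | any cost) under each arm, and average the difference.
2. Use baseline covariates only in both parts. The planned models also adjust for clinical outcomes, which mentoring may change; predictions that keep them would not give the total effect over all randomised women.
3. Take a 95% confidence interval from the bootstrap already planned, resampling whole women and refitting both parts each time.
4. Report the two part coefficients as descriptive, with no cost conclusion from the conditional part alone.

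Some zeros may reflect care received outside MUSC. The recombined result includes them, so it should be labelled as an effect on MUSC costs.

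The cost is a few sentences in the plan and a little more analysis work. The interval may look less favourable than the result of a single part.

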Using QALYs, the incremental cost-effectiveness ratio (ICR) can be calculated as: (QALYintervention-QALYcontrol)/(Costintervention-CostControl). The ICR can then be compared with the ICRs for previous lupus interventions. We will take the perspective of the provider, insurer and patient. All three are affected in the hospitalization charges since insurers pay part and patients will pay part of the charges. In addition to the main cost-effectiveness outcome of QALY and the ICR, costs of the

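### The Aim 3 cost-effectiveness ratio is to be reported without uncertainty, although it rests on a QALY difference estimated from sampled participants, and no rule is given for judging Hypothesis 3

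*Combined protocol and SAP*

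**What the plan says.** Hypothesis 3 (opening aims section, AIM 3) is directional: compared with the support-group control, peer mentoring will be cost effective, measured in QALYs.

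The AIM 3 text of the Overview of Statistical Analysis Plan derives QALYs for each arm from the SF-36 measured 12 months after baseline, by a cited published method. It then says that "the incremental cost-effectiveness ratio (ICR) can be calculated as: (QALYintervention-QALYcontrol)/(Costintervention-CostControl"), and that "The ICR can then be compared with the ICRs for previous lupus interventions". QALYs and this ratio are called the main cost-effectiveness outcome ("In addition to the main cost-effectiveness outcome of QALY and the ICR, costs of the", after which the sentence turns to utilization costs). On perspective: "We will take the perspective of the provider, insurer and patient".

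On uncertainty the plan is explicit: "The ICR will be reported as a single ratio with no uncertainty attached to it". It infers from this that "standard statistical characteristics such as confidence intervals or hypothesis test to compare it to an a priori ICR from another study are not applicable". The only resampling planned is described as follows: "Bootstrapping methods will be used to conduct sensitivity analyses for all cost models". The only other interpretive text is "We will calculate the ICR and a clinically relevant interpretation of the outcome". That sentence is split in the extracted text. Its ending, which follows the eligibility criteria, says only that the interpretation will follow other published studies.

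**The concern.** Printing one number does not remove the error in it. The plan itself treats closely related data differently. The Aim 1 analysis promises 95% intervals for the quality-of-life effect, and the Aim 1 outcomes section says the LUP-QOL incorporates the SF-36. The QALY ratio built on the SF-36 gets no interval.

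At stake is how Hypothesis 3 will be judged. The plan invites comparison with ratios from earlier lupus interventions but rules out any formal version of that comparison. It names no threshold, reference ratio or decision rule. A favourable point value could therefore be taken as support for the hypothesis however imprecise it is, with the standard of judgement chosen after the ratio is known.

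**Working it through.** **1. Figures the plan gives.** Aim 3 states no QALY SD, cost variance, willingness-to-pay value or precision target, so there is no Aim 3 figure to reproduce. The usable inputs are:

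- 150 mentees per arm (Study Overview);
- 20% attrition at 12 months and a 0.35 SD effect on quality of life (Power and Sample Size Justification).

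That section's 123 per group can be reproduced for a baseline-to-12-month change with correlation 0.6, two-sided 5% level and 80% power:

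- SD of change = sqrt(2 × (1 − 0.6)) = 0.894
- n = 2 × 0.8 × (1.960 + 0.842)² / 0.35² = 102.5
- 102.5 × 1.2 = 123.0

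This confirms the scale of the 0.35 SD effect. It was set for quality of life, and its use for QALYs below is my assumption.

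**2. Precision of the QALY difference.** Completers per arm: 150 × 0.8 = 120. In units of the QALY SD, for an unadjusted comparison of independent participants:

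- SE = sqrt(2/120) = 0.129
- 95% half-width = 1.96 × 0.129 = 0.253
- At 0.35 SD, relative SE = 0.129/0.35 = 37%

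**3. Effect on the ratio.** If the cost difference is a fixed positive amount, the ratio is the QALY difference divided by a constant, so its limits scale directly.

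| Completers per arm | Observed QALY difference (SD) | 95% CI (SD) | Upper/lower limit |
|---|---|---|---|
| 120 | 0.50 | 0.247 to 0.753 | 3.0 |
| 120 | 0.35 | 0.097 to 0.603 | 6.2 |
| 120 | 0.20 | −0.053 to 0.453 | crosses zero |
| 150 (no attrition) | 0.35 | 0.124 to 0.576 | 4.7 |
| 98 (123 less 20%) | 0.35 | 0.07 to 0.63 | 9.0 |

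With 120 per arm, any observed difference below 0.253 SD has an interval that includes no gain.

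**4. If cost also varies.** Any utilization charges in the denominator also come from sampled participants. With independent normal draws (400,000) and an assumed coefficient of variation for the cost difference, the central 95% range of the ratio, as a multiple of its value at 0.35 SD, is:

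- fixed cost: 0.28 to 1.72
- coefficient of variation 0.25: 0.26 to 2.4
- coefficient of variation 0.5: −0.03 to 6.2

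**5. Does other text supply the missing uncertainty or rule?** The bootstrap sentence is confined to cost models and does not reach the QALY difference or the ratio. The sentence excluding uncertainty comes after it and is specific to the ratio. Neither the comparison with earlier interventions nor the completed interpretation sentence contains a criterion.

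**The case against.** The best defence is that the ratio is descriptive. The plan disclaims a formal test, a confidence interval for a ratio is awkward, and the quality-of-life effect will have its own interval beside it. Part of this stands: a reader would see a null quality-of-life result. It does not rescue the inference that intervals are inapplicable. The ratio is named as part of the main cost-effectiveness outcome and serves a directional hypothesis. The awkwardness of ratio intervals is a reason to report the two differences and net benefit, not to report nothing.

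Several stronger readings are tempting, and the documents do not support them:

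- *A null quality-of-life effect would be hidden.* It would not, because the Aim 1 analysis plans intervals for it.
- *One can state how often a worthless programme would pass a dollar benchmark.* That needs a QALY SD, a programme cost and a benchmark. None is given, and the plan has no such pass rule, so these rates cannot establish severity.
- *The interval will include QALYs lost.* That depends on the result. At the plan's own 0.35 SD the interval excludes zero.
- *The cost term is a fixed programme cost.* The Methods for AIM 3 describe programme costs, and the analysis text presents utilization costs as an addition to the ratio. Yet the sentence following the choice of perspectives refers to hospitalization charges. The term is unclear.
- *The formula is upside down.* QALYs over cost agrees with the plan's own description of QALYs gained relative to cost. It misleads only if set beside a ratio expressed the other way.
- *QALYs rest on the month-12 value alone.* The plan does not say so, and it leaves the calculation to a cited method that is not available here.

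**Conclusion.** The concern holds. The statements that the ratio carries no uncertainty, and that intervals or tests therefore do not apply, are wrong as written, and Hypothesis 3 has no prespecified rule.

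On the plan's planned enrolment, attrition and 0.35 SD effect, the limits of the ratio differ about 6-fold with cost fixed. The figure runs from about 3-fold at an observed 0.50 SD to an interval crossing zero at 0.20 SD. This size rests on using the quality-of-life effect as a stand-in for QALYs, on an unadjusted comparison and on independent participants. Baseline adjustment or clustering by mentor would change it. The existence of sampling error depends on none of these assumptions.

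This should be fixed before analysis. It does not affect the sample size or the analyses for Aims 1 and 2.

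**What to change.** In the AIM 3 analysis text:

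1. Delete the sentence excluding uncertainty and the one declaring intervals and tests inapplicable.
2. Bootstrap participants jointly for the cost and QALY differences, and report each difference with a 95% CI.
3. Show the joint uncertainty on the cost-effectiveness plane, or as net benefit over a stated willingness-to-pay range. This also avoids an ambiguity of the ratio: it is negative both when QALYs are gained at lower cost and when they are lost at higher cost.
4. State in advance, on that basis, how Hypothesis 3 will be judged.

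Three points need clarification only:

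- whether the cost term is programme cost, utilization charges or both, and whether support-group cost enters the control-arm cost;
- that the ratio will be put in the same orientation as any published ratio it is compared with;
- how the cited QALY method uses the SF-36 visits and the baseline value.

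The cost is revised wording and a little more programming on data already due to be collected. The team must commit to a willingness-to-pay range and a rule before seeing the result, and must accept that the interval may be wide.
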